5.1.2 Risk of Study Procedures

The collection of the research data from history and physical examination such as body weight, height and vital signs carries minimal risk. Intravenous blood sampling risks of bruising, infection, anemia, and fainting are common. The clamp study involves likely risk of discomfort associated from two venipunctures. The infusion of 20% sugar water during the clamp may cause local tissue damage if it leaks outside the vein. However, the chances for this happening are minimal because of very close observation by the nurse and doctor. Hematoma formation and hypoglycemia are rare complications, which we have not had since clamp experiments were initiated 16 years ago. The stable isotope glucose tracer in the amount used has no hazardous effects.

The risks of percutaneous muscle biopsy are bleeding and infection (both rare), bruising (infrequent) and discomfort (likely). With the use of a local anesthetic, our subjects describe the

discomfort of muscle biopsy as about twice that of intravenous cannulation. Some residual stiffness in the vastus lateralis can persist for 1-2 days (common). An elastic wrap and ice bag are applied post-biopsy to decrease the risk of bruising and for an anesthetic effect. In our experience using similar protocols, subjects have not experienced any adverse effects from these procedures other than a small amount of residual localized soreness at the biopsy site. Additional risk includes any unusual reaction to the elastic bandage wrap and ice, i.e. leg numbness which would indicate the elastic bandage had been applied too tightly or the ice left on too long; or any skin redness, irritation, and chafing from the applied antibiotic ointment and/or steri-strips.

The exercise test ($VO_2\max$) and subsequent exercise training sessions may cause muscle soreness or fatigue, but in adults without a known history of heart disease, the risk of heart attack or death from maximal or sub-maximal exercise bouts is rare. The relative risk of exercise testing for obese adults has not been clearly defined. However, a survey of more than 2,000 clinical exercise testing laboratories, in which more than 600,000 tests were performed, showed a death rate of approximately 1 per 20,000.

American College of Sports Medicine (ACSM) criteria will be used to halt exercise testing. In addition to ACSM criteria, the exercise test will be stopped if the subject has either signs or symptoms of cardiovascular compensation, e.g. hypotensive response to exercise. These exercise tests will be interpreted by a physician at the University of Pittsburgh Medical Center. The staff conducting maximal exercise tests are ACLS certified. The Exercise Physiology Laboratory has a crash cart with emergency equipment (including a defibrillator-monitor, airway equipment, IV sets and fluids, syringes, needles, Lidocaine, Epinephrine, Nitroglycerine, etc.) and will be present during maximal exercise testing.

The radiation dose of the whole body DEXA is approximately 3 mrems. For comparison, adult radiation workers are permitted, by Federal regulation, to receive a maximum whole body radiation dose of 5000 mrems/year and a maximum single organ radiation dose of 50,000 mrem/year. There is no minimum level of radiation exposure that is considered totally free of the potential risk of causing genetic changes (cellular abnormalities) or cancer. However, the risk associated with the amount of radiation exposure that the subject will receive from participation in this research study is considered to be low and comparable to everyday risks. Menstruating females in the reproductive age group must have a negative pregnancy test within 24 hours prior to each of these studies in order to reduce the potential for exposing a fetus to radiation.

During the FMD test, the occlusion cuff will be placed on a subject's arm and will stay inflated for 5 minutes. The cuff could cause minor pain, possible bruising, numbness, tingling and irritation to the patient's skin. The subject will be asked to lie still on their back for 30 minutes during the test; this could cause stiffness or dizziness.

The risks associated with carotid Intima-Media Thickness (IMT) and Pulse Wave Velocity measurements are rare and include mild discomfort at the sites on the neck or groin where the ultrasound probe or tonometer are placed or sites on the neck, chest or groin where the skin is marked with a marker. The ECG electrodes will stick to the subject's skin and sometimes, when the electrodes are pulled off, the subject can experience slight irritation of the skin.

The risks associated with the ambulatory blood pressure monitor (ABPM) are rare and include a feeling of pressure, bruising, or irritation at the site where the blood pressure cuff is worn.

There is a potential risk of stress and anxiety while participating in this study. It is likely that at least mild anxiety will occur while the subject is hospitalized to participate in this study. There is a potential of developing an infection (viral or bacterial) while in the hospital because of exposure to sick patients. We will try to not pair participants to share a hospital room with a sick patient. Participants will not have tests that have more than a minimal risk of causing an infection. In our experience, the risk of developing an infection while at the CTRC is minimal.

5.2 ALTERNATIVE TREATMENTS

The alternative treatments for the subjects participating in this investigation are to continue their medical care under the direction of their primary physicians.

5.3 POTENTIAL BENEFITS

Participation in the proposed research may or may not provide a direct benefit to participants in this research. This research involves an intervention or procedure that presents greater than minimal risk to the involved adults, but which holds out the potential for direct individual benefit. The risk is justified by the extent of potential benefit to the involved adults; which includes possibly revealing previously-undiagnosed morbidities commonly seen in obesity such as hyperlipidemia, impaired fasting glucose, or type 2 diabetes mellitus. In addition, they will have their percentage and distribution of body fat assessed by DEXA, an important piece of information should the individuals choose to enter a weight management program after the completion of the study. This data has also been shown to predict cardiovascular and diabetogenic risk, information that is important for an overweight/obese subject. Also, assessments of baseline cardiovascular health will be made. This data is important for these overweight/obese subjects. Information obtained from the proposed research will provide information about the relationship between metabolic syndrome and hypertension treatment and patient outcome.

Based on the preceding assessment of risks and potential benefits, the risks to subjects are reasonable in relation to anticipated benefits. The research presents a balance of risks and expected direct benefits similar to that available in the clinical setting.

5.4 DATA SAFETY MONITORING PLAN

5.4.1 Data Safety Monitoring Board

The local Data Safety Monitoring Board (DSMB) will be comprised of members including experts in endocrinology, exercise physiology, clinical research, and clinical trial design, biostatistics, and research ethics. The DSMB will conduct interim monitoring of accumulating data from research activities to assure the continue safety of human subjects, relevance and appropriateness of the study, and the integrity of research data.

5.4.2 Data Safety Monitoring Plan

Assuring patient safety is an essential component of this protocol. The study Investigator has primary responsibility for the oversight of the data and safety monitoring. The study sub-investigators will evaluate all adverse events. All subjects who have AEs, whether considered associated with the use of the study medication or not, must be monitored to determine the

outcome. The clinical course of the AE will be followed up according to accepted standards of medical practice, even after the end of the period of observation, until a satisfactory explanation is found or the Investigator considers it medically justifiable to terminate follow-up.

The study coordinators must view patient records for possible adverse events until 72 hours after the last dose of study drug. All untoward medical occurrences observed in subjects receiving the study drug will be recorded on the participants' adverse event case report forms (CRF) by the study coordinator under the supervision of the Investigator. The CRFs will then be reviewed for completeness and internal consistency. Subsequently, the CRFs will be recorded on an electronic password-guarded study database. The electronic database that is being used for the purpose of this study has not been fully validated to be in compliance with the FDA regulations at 21 CFR Part 11; i.e. taking into account the limited scope of this clinical investigation. In addition to internal safeguards built into a computerized system, external safeguards will be put in place to ensure that access to the computerized system and to the data is restricted to authorized personnel. Training conducted by qualified individuals on a continuing basis will be provided to individuals in the specific operations with regard to computerized systems that they are to perform during the course of the study.

The Investigator will work with the reporting sponsor and sub-investigator to prepare a detailed written summary of serious, unexpected, and treatment related adverse events, and will compare, and contrast the event with prior events. The detailed written summary will be provided to the local DSMB and the IRB.

In addition, the DSMB Report addressing the following information will be submitted to the IRB at the time of continuing review annually or more often as required:

- A list of the research personnel who participated in the data and safety monitoring.
- The frequency of monitoring that took place during the renewal intervals and/or the dates that data and safety monitoring was conducted.
- A summary of cumulative data related to unanticipated problems (including adverse events) including a determination of causality and whether the risk to benefit assessment has changed.
- If appropriate, a summary of pertinent scientific literature reports, therapeutic developments, or results of related studies that may have an impact on the safety of study participants or the ethics of the research study.
- A summary of the outcome of reviews conducted to ensure subject privacy and research data confidentiality.
- Final conclusions regarding changes to the anticipated benefit-to-risk assessment of the study participation and final recommendations related to continuing, changing, or terminating the study.

Stopping Rule:

For safety reasons, we propose to discontinue this study protocol once 2 subjects enrolled experience one of two of the following on repeat PK testing despite appropriate nitrite dose reduction as follows:

1. Methemoglobin greater than 5%. A nitrite dose reduction is proposed from 40 mg three times daily to 20 mg three times daily if this methemoglobin % is reached at any study visit. Two hour PK testing will be repeated on a separate day at the lower nitrite dose once two subjects have reached this initial methemoglobin threshold. If methemoglobin is greater than 5% on the lower nitrite dose, participation in the study for the subject will be discontinued.
2. Mean arterial pressure (MAP) decrease <55 mmHg, or if subject's baseline MAP is <60, and there is a decrease greater than or equal to 20% from their baseline (on the morning of receiving study drug). A nitrite dose reduction is proposed from 40 mg to 20 mg three times daily if this MAP threshold is reached. Two hour PK testing will be repeated on a separate day at the lower nitrite dose once two subjects have reached this initial MAP threshold. If MAP remains <55 mmHg or in the case of the subject with a baseline MAP <60, then if MAP decrease is greater than or equal to 20% from baseline on the lower dose, subject participation in the study will be discontinued.
3. Positive pregnancy test.
4. In the event that the medication compliance rate is <80%, subjects will be re-educated on medication compliance. If medication compliance repeatedly falls outside of the acceptable range, the study investigators will discuss subject eligibility for continued participation in the study.

If an unexpected fatal event or any of the above three life-threatening events occur despite dose reduction, the study will be halted, until data review by investigators and the Data Safety Monitoring Board has rendered a final recommendation about study continuation.

5.4.3 Parameters to be Monitored

The following progress will be monitored throughout the course of the research to ensure the safety of subjects as well as the integrity and confidentiality of their data.

- An evaluation of the progress of the research study, including subject recruitment and retention, and an assessment of the timeliness and quality of the data.
- A review of collected data (including adverse events, unanticipated problems, and subject withdrawals) to determine whether there is a change to the anticipated benefit-to-risk assessment of study participation and whether the study should continue as originally designed, should be changed, or should be terminated.
- An assessment of external factors or relevant information (eg. pertinent scientific literature reports or therapeutic development, results of related studies) that may have an impact on the safety and study participants or the ethics of the research study.
- A review of study procedures designed to protect the privacy of the research subjects and the confidentiality of their research data.

The severity of adverse changes in physical signs or symptoms will be classified as follows:

- Grade 1 (Mild): asymptomatic or mild symptoms; clinical or diagnostic observation only; intervention not indicated.

- Grade 2 (Moderate): minimal, local or noninvasive intervention indicated; limiting age-appropriate ADL (Activities of Daily Living).
- Grade 3 (Severe): medically significant but not immediately life-threatening; hospitalization or prolongation of hospitalization indicated; disabling; limiting self care ADL.
- Grade 4 (Life-threatening): consequences; urgent intervention indicated.
- Grade 5 (Death): event is a direct cause of death.

5.4.4 Frequency of Monitoring

The Investigator will review subject safety data as it is generated. The Investigator, sub-investigators, and the research staff will meet on a two week interval to re-evaluate study goals, subject recruitment, data coding and retention, documentation and identification of adverse events, complaints and confidentiality of subjects. There will be an evaluation of the progress of the research study, including assessments of data quality, time lines, participant recruitment, accrual, and retention. The Investigator will also review the outcome and adverse event data to determine whether there is any change to the anticipated benefit-to-risk ratio of study participation and whether the study should continue as originally designed or should it be re-evaluated and changed.

The DSMB will also be expected to meet as needed, but not less than, every six months to provide an overall summary status report to the regulatory agencies.

5.4.5 Reportable Adverse Events

For this study, a serious adverse event is any untoward clinical event that is thought by the investigator to be study-related, that is also:

1. Fatal or immediately life threatening
2. Permanently disabling, or severely incapacitating.
3. Requires or prolongs inpatient hospitalization.
4. Important medical events that may not result in death, be life threatening, or require hospitalization may be considered serious adverse events when, based upon appropriate medical judgment, they may jeopardize the patient, or subject, and may require medical, or surgical intervention to prevent one of the serious outcomes listed above.

If clinically important and unexpected adverse experiences, or clinically important study-related adverse experiences occur, they will be recorded on the adverse event case report form.

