Based on the above PK and the differential BP effects with single doses of sodium nitrate vs. nitrite, the published 10-week oral nitrite trial and preliminary findings in this combined trial, we propose to remove sodium nitrate, which is the second potential depot of nitrite. Therefore, we need to administer a greater nitrite load since the previous two sources combined (sodium nitrate and nitrite) in the first 5 subjects of this study did not result in any BP lowering (Fig 1A-C). Similar to our prior dosing modification (when we titrated from sodium nitrite 20 mg once daily to 20 mg twice daily), we propose a step-up dosing in the first 3 subjects enrolled whereby we will begin with sodium nitrite 20 mg TID daily and after 2 weeks on this dosing and if no SAE, increase to 40 mg TID for the remaining 10 weeks of the study, given the PK of the drug and to induce blood pressure lowering in our hypertensive subjects. After three subjects have completed this regimen, then we propose that from the start, all remaining subjects start on sodium nitrite 40 mg TID and continue for all 12 weeks.

Although we are increasing the dose/frequency of sodium nitrite, since we are discontinuing sodium nitrate (which is reduced to nitrite in our body as was confirmed in our Phase I PK study), we are continuing our in-person safety monitoring visits to assess for adverse events at every other week. We will continue alternating every other week phone visits to assess compliance and for adverse events. Our two safety outcomes are methemoglobin by non-invasive co-oximetry and mean arterial pressure (MAP) obtained through 3 automated resting BP measurements 30-45 min following morning nitrite dosing and averaging the final 2 of 3 MAPs.

Based on the Joint FAO/WHO ADI for sodium nitrate and nitrite, the above DASH diet patterns, and the recently observed human and rodent effects of nitrate and nitrite on blood pressure and

glucose homeostasis, including our PK/PD trial of single doses of oral nitrate and nitrite, the existing inhaled nitrite trial, and this open label trial safety and lack of BP reduction findings following a total of 5 subjects' completion, the study investigators believe that a safe and likely therapeutically effective dose of sodium nitrite will be 40 mg three times daily (~1.26 mg/kg body weight per day for a 95 kg subject). Our sodium nitrite dose selection is equivalent to 12.6 times the ADI.

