A recent study determined the safety and feasibility of prolonged intravenous nitrite infusion. Twelve adult volunteers received increasing starting doses of sodium nitrite, 4.2 to 533.8 µg/kg/hr for 48 hours. Dose limiting toxicity occurred at 445.7 µg/kg/hr (10.6 mg/kg/day) and was limited to asymptomatic transient decreases of arterial blood pressure of up to 20 mmHg and asymptomatic increases of methemoglobin levels above 5%. No tolerance or clinically significant rebound was observed³⁶. Note, this is 8.2 times the daily dose we plan to use in this trial (based on an adult body weight of 95 kg).

For nitrite, two retrospective case-control studies have shown that high maternal dietary nitrite intake from cured meat or drinking water during pregnancy might be associated with risk of childhood brain tumors and possibly gastric and esophageal cancer. This evidence is only based on retrospective case-control studies; cohort studies have found no significantly increased risks²⁴.

In the 2001 National Toxicology Program (NTP) Report summarizing 2-year rodent drinking water studies, there was no evidence of carcinogenic activity of sodium nitrite in male or female F344/N rats exposed to up to 130 mg/kg/day in males and 150 mg/kg/day in females, or in male B6C3F1 mice exposed to up to 220 mg/kg/day. There was equivocal evidence of carcinogenic activity of

sodium nitrite in the highest dose of 165 mg/kg/day in female B6C3F1 mice based on the positive trend in the incidences of squamous cell papilloma or carcinoma (combined) of the forestomach. Exposure to sodium nitrite in drinking water resulted in increased incidences of epithelial hyperplasia in the forestomach. However, no chromosomal damage (genetic toxicity) was observed in three studies conducted in rats and mice *in vivo*³⁷. Taken together, these findings suggest minimal carcinogenic nitrite-mediated risk.

In the current study, we will use much lower doses of nitrite than used safely in any of these studies. Our nitrite dose of 20 mg three times daily stepping up to 40 mg three times daily is lower than the dose used on the cardiovascular IND and <40% of the dose for cyanide poisoning.

To summarize, we anticipate the following symptoms by organ system and likely frequency of risk:

Gastrointestinal

- Common: none
- Frequent: none
- Infrequent: dry mouth
- Rare: nausea, abdominal pain, and vomiting

Hematologic

- Common: none
- Frequent: none
- Rare: methemoglobinemia

Cardiovascular

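### Section 5.4.5 makes study-relatedness a condition of being a serious adverse event, which narrows the SAE label and the dose step-up condition that relies on it

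*Combined protocol and SAP*

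**What the plan says.** Section 5.4.5 (Reportable Adverse Events) opens its definition with "a serious adverse event is any untoward clinical event that is thought by the investigator to be study-related, that is also" and then lists four criteria: fatal or immediately life-threatening; permanently disabling or severely incapacitating; requiring or prolonging inpatient hospitalisation; and other important medical events that may need intervention. The protocol gives no other definition of an SAE.

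Section 5.4.2 (Data Safety Monitoring Plan) treats relatedness differently. On follow-up it says "All subjects who have AEs, whether considered associated with the use of the study medication or not, must be monitored". On recording it says "All untoward medical occurrences observed in subjects receiving the study drug will be recorded" on the adverse event case report form (CRF). The investigator prepares a "detailed written summary of serious, unexpected, and treatment related adverse events", and the report to the IRB summarises cumulative data "including a determination of causality and whether the risk to benefit assessment has changed".

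Section 2.2.2 (Dose Selection) uses the label in a decision. The first three subjects enrolled start at 20 mg three times daily and, "after 2 weeks on this dosing and if no SAE, increase to 40 mg TID". Once three subjects have completed that regimen, all remaining subjects start at 40 mg three times daily. Section 5.1.1 also describes the step-up ("Our nitrite dose of 20 mg three times daily stepping up to 40 mg three times daily") but does not mention the SAE condition.

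**The concern.** Seriousness describes what happened to the subject. Relatedness is a judgement about why. Section 5.4.5 merges the two, so an event with a serious outcome counts as an SAE only if the investigator attributes it to the study.

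This matters more here than in a blinded, controlled trial. The synopsis states a safety aim, and section 2.1 describes an open-label, non-randomised study in which every subject takes nitrite. The person deciding on relatedness knows that the subject is on drug, and there is no concurrent group in which to see how often such events occur without it. A statement that the study had no SAEs would mean only that the investigator attributed no serious event to the study, and a reader could not tell this from the term. The protocol itself leans on such statements: section 2.2.2 cites the absence of serious adverse events in two earlier studies in support of its dose.

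**Working it through.** No event-rate calculation applies. The documents give no expected number of SAEs and plan no SAE analysis. The check is to take each rule that might use the definition and ask whether the relatedness clause changes what the rule does.

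**Reach within the definition.** The clause stands ahead of the list and is joined to it, so it governs 4 of 4 criteria.

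**Reach across the protocol.**

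| Rule | Section | Uses the SAE label or seriousness? | Own relatedness term? | Changed by the clause? |
|---|---|---|---|---|
| AE follow-up | 5.4.2 | No | Explicitly disregards it | No |
| AE recording | 5.4.2 | No | None | No |
| Written summary to DSMB and IRB | 5.4.2 | Yes | Yes | No, if its three adjectives are joint conditions |
| Methemoglobin and mean arterial pressure rules | 5.4.2 | No | None | No |
| Halt for an unexpected fatal event | 5.4.2 | No | None | No |
| Severity grading | 5.4.3 | No | None | No |
| 24-hour report to DSMB and IRB | 5.4.6 | No | Yes | No |
| FDA 7-day notice | 5.4.6 | No | None | No |
| Serious and unexpected events to DSMB and IRB, with the 15-day written FDA report | 5.4.6 | Yes | Yes | No |
| Planned analyses | 2.6 | No | None | No |
| Step-up after 2 weeks | 2.2.2 | Yes | None | **Yes** |

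Counting section 5.4.6 by paragraph, with the 15-day report inside the third, 2 of the 3 event-reporting rules carry their own relatedness term and 1 carries none. None of the three needs the clause in 5.4.5. Where seriousness and association with the drug are both required, the clause is redundant. This suggests that those sections were written with relatedness as a separate attribute.

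**The step-up condition.** The direct reach is at most 3 subjects. Against the planned sample of 30 in the synopsis, that is 3/30 = 10%. Section 3.1 speaks of twenty subjects, and on that figure it is 3/20 = 15%. The documents do not say whether the first five subjects, treated on an earlier combined regimen, count toward the 30, so the percentage is only a rough guide. The indirect reach is wider. The other subjects (30 − 3 = 27 on the synopsis figure) start at the higher dose after three have completed the regimen. A serious event judged unrelated in one of the three would not engage the condition and so would not, through it, hold back that completion.

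**The recording sentences.** Section 5.4.2 sends every untoward occurrence to the CRF. The last sentence of 5.4.5 names, for the same form, only events of clinical importance that are either unexpected or related to the study. An event that is serious, unrelated and expected falls under 5.4.2 but under neither part of the 5.4.5 sentence.

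**The case against.** The strongest reply is that little turns on the clause. Adverse events are followed whatever their cause, the reporting rules bring their own relatedness terms, and no SAE analysis is planned. The halt rule, "If an unexpected fatal event or any of the above three life-threatening events occur despite dose reduction, the study will be halted", applies without reference to the SAE label. The DSMB reviews accumulating data at least every six months, the study team meets every two weeks, and both see adverse events in general. Section 5.4.5 is headed as concerning reportable events, so it could be read as a reporting filter in line with 5.4.6. There is also no outright contradiction with 2.2.2, which simply uses a term that 5.4.5 defines.

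Most of this stands, and it limits the size of the point. Three parts do not remove it. First, the sentence defines the term for the whole study, and 5.4.6 sets the reporting rules separately. Second, the assurance that unrelated serious events are still recorded rests on 5.4.2 and is weakened by the narrower CRF sentence in 5.4.5. Third, the 2.2.2 condition has no relatedness term of its own, so the definition alone decides what it covers.

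A reader might infer more: that unrelated deaths and hospitalisations go unrecorded, that expedited reporting fails, or that the trial's results are biased. The documents do not support this. Section 5.4.2 requires recording and follow-up of all events. The 5.4.5 CRF sentence is inconsistent with that but does not say that other events are left out. The FDA 7-day sentence and the fatal-event halt carry no relatedness condition, and sample size, significance level and the primary analysis are untouched. A reader might equally infer that the effect stops at three subjects. The sentence in 2.2.2 about the remaining subjects does not support that either.

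**Conclusion.** The point holds at moderate weight: the definition should be corrected, but the trial's validity does not depend on it. The clause governs all four seriousness criteria. It directly affects the SAE label, any SAE statement made from the study, and one stated decision in the first three subjects, and it indirectly affects the starting dose of those who follow. It changes no reporting rule in 5.4.6, no methemoglobin, arterial-pressure or fatal-event rule, and no planned analysis.

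Two assumptions support this. The abbreviation in 2.2.2 is taken to mean the term defined in 5.4.5. The written summary in 5.4.2 is read as covering events that are serious, unexpected and treatment-related all at once, which is the more natural reading and matches 5.4.6. If those were three separate categories, serious events that are unrelated and expected would also drop out of that summary under the 5.4.5 definition.

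**What to change.** - In 5.4.5, delete the relatedness clause and define an SAE by the four listed criteria alone.
- Record relatedness as a separate field on the adverse event CRF, and report SAEs overall and by relatedness.
- Bring the last sentence of 5.4.5 into line with the recording rule in 5.4.2.
- Leave 5.4.6 as it stands. The DSMB and IRB paragraphs already have their own relatedness term, and none should be added to the FDA 7-day sentence.
- Deleting the clause changes by default what SAE means in the 2.2.2 step-up condition. The sponsor must therefore state, in the same amendment, which events that condition covers, and reconcile 2.2.2, 5.1.1 and 5.4.5. Nothing here says what that clinical rule should be.

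The cost is small: one clause and one sentence in 5.4.5, a clarifying phrase in 2.2.2, a CRF field if none exists, and one line on SAE reporting. The downsides are slightly more SAE paperwork and the need to restate the step-up condition at the same time.
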